## **15. Leading Phase of Trial for Site Selection**

Candidate sites for trial will be initially identified based on hospital grades, the intervention experience, and the volume of revascularization surgery cases. It will take three months before the trial kickoff for the steering committee to assess site research capability and commitment to the study. The center meeting the following criteria will be enrolled into the trial: ① at least 5 cases will be recruited within the leading phase; ② the rate of perioperative complications should be not more than 15% (stroke or death).

## **16. Schedule of Follow-up and Post-study Follow-up Period**

All patients will be followed up until the primary endpoint or the end of the trial. Complete endpoint information will be obtained with the best effort irrespective of

patient study status, unless patients withdraw consent to participate the trial. Patients will continue to be followed up beyond date of consent withdrawal if they stop the trial and receive other treatment such as medical therapy but agree to provide the prognostic information. The face-to-face interview will be performed by study neurologists at discharge, at 3 months, at 6 months and at 12 months (or by telephone) after the recruitment of patients. If they are more convenient to have access to the study site near to their living areas, patients will be allowed to go to the site for their follow-up.

Visits	Windows	Definition
Randomization	0 day	Study Day 0 day
At discharge	0 day	Based on the number of hospitalization days
At 3 month	7 days	Day 83-97
At 6 months	14 days	Day 166-194
At 12 months	30 days	Day 330-390

Note: 1 month= 30 days

The following procedures will be done at 3 months, at 6 months after enrollment:

- ✧ A neurological evaluation will be performed (Modified Rankin Scale, National Institute of Health Stroke Scale, modified Barthel Scale);
- ✧ A physical examination will be performed, including vital signs (blood pressure, heart rate);
- ✧ Information will be collected on medications, risk factors, and events of interest since the last visit;
- ✧ Computed Tomography Perfusion (CTP), Magnetic Resonance (MR) and Digital subtraction angiography (DSA) will be performed;

The following evaluations will be done at the end of trial:

- ✧ Lab tests for diabetic control and hyperlipidemia management will be performed;
- ✧ A neurological evaluation will be performed (Modified Rankin Scale, National Institute of Health Stroke Scale, modified Barthel Scale);
- ✧ A cognitive function evaluation will be performed (MoCA);
- ✧ Computed Tomography Perfusion (CTP) and Magnetic Resonance (MR) will be done if a patient does not experience a primary endpoint before the end of trial. Images will be transferred to the core imaging evaluation lab.
- ✧ Information will be collected on medications, risk factors, and events of interest since the last visit;

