### **6.2. Clinical Secondary Endpoint**

- All kinds of adverse events related to surgery within 30 days
- Infarctions on the contralateral side within 1 year of randomization
- Transient ischemic attack on the surgically treated side within 1 year of randomization

- The changes from baseline in CBF measured by ASL at 7 days, 3 months, 6 months, 12 months or end of trial
- The changes from baseline in modified Rankin Scale (mRS) at 7 days, 3 months, 6 months, 12 months or end of trial
- The changes from baseline in National Institute of Health Stroke Scale (NIHSS) at 7 days, 3 months, 6 months, 12 months end of trial
- The changes from baseline in modified Barthel Scale at 7 days, 3 months, 6 months, 12 months or end of trial

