### **Post study Follow-up Period**

All patients will be followed every 12 months by study personnel after the EoT. Any treatment beyond the EoT is at the discretion of the treating physicians. The primary or secondary endpoints will be collected every 12 months since the EoT by telephone interview.

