**modified Rankin Scale**

The modified Rankin Scale (mRS) is a scale commonly used for measuring the degree of disability or dependence in the daily activities of individuals who have suffered a stroke, and it has become the most widely used clinical outcome measure for stroke clinical trials.

Description	Score (select one)
No symptoms at all	0 
No significant disability despite symptoms; able to carry out all usual duties and activities	1 
Slight disability; unable to carry out all previous activities, but able to look after own affairs without assistance	2 
Moderate disability; requiring some help, but able to walk without assistance	3 
Moderately severe disability; unable to walk without assistance and unable to attend to own bodily needs without assistance	4 
Severe disability; bedridden, incontinent and requiring constant nursing care and attention	5 

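### Section 16 contradicts itself on whether clinical assessments continue after a primary endpoint; read literally, its opening sentence would cost the survivors of an event their later secondary-endpoint data

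*Protocol*

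**What the plan says.** **Text that ends follow-up at the event.** Protocol Section 16 begins: "All patients will be followed up until the primary endpoint or the end of the trial".

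**Text that implies follow-up goes on.**
- The next sentence of Section 16: "Complete endpoint information will be obtained with the best effort", whatever the patient's study status, unless consent is withdrawn.
- The Section 16 procedure lists for 3 and 6 months and for the end of the trial each include "A neurological evaluation will be performed (Modified Rankin Scale, National Institute of Health Stroke Scale, modified Barthel Scale"), with no condition on being event-free.
- The Schedule of Visits and Tests marks mRS, NIHSS and Barthel at discharge, 3 months, 6 months, 1 year and the event visit, again without condition.
- Post study Follow-up Period: "All patients will be followed every 12 months by study personnel after the EoT", with primary or secondary endpoints collected by telephone.
- Section 21.2 includes all randomized patients irrespective of continued participation and analyses all efficacy variables in that set.

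**What depends on it.** Section 6.2 lists "The changes from baseline in modified Rankin Scale (mRS) at 7 days, 3 months, 6 months, 12 months or end of trial", with NIHSS and Barthel on the same time points. It also lists TIA on the treated side and contralateral infarction within 1 year (2 years in the synopsis).

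**The concern.** The reference to the primary endpoint in the opening sentence of Section 16 has no function unless reaching that endpoint ends follow-up. Staff could reasonably apply it that way. Section 17 adds to the impression by saying that treatment after a primary endpoint is no longer monitored.

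Under Section 6.1, any stroke within 30 days of surgery is a primary endpoint, and Section 3 places the highest stroke risk in that same window. A surviving patient with a stroke on day 5 would then have no 3-, 6- or 12-month scores and no record of later TIA or contralateral infarction. Surgery-related adverse events in the rest of the 30 days, another secondary endpoint, could be missed too.

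These data would be missing because of the outcome, and more often in the arm with more events. The functional comparison would lose the patients in whom surgery did most harm. A SAP can say how missing values are handled, but it cannot recover visits that were never made. The rule therefore has to be settled in the protocol.

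**Working it through.** The protocol gives no figure to reproduce on this point. The check has two parts.

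**1. Which reading do the passages favour?**

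| Place | Does assessment continue after a primary endpoint? |
|---|---|
| Section 16, opening sentence | No |
| Section 16, next sentence | Yes for endpoint information; visits not mentioned |
| Section 16, 3- and 6-month and end-of-trial neurological evaluation | Yes (no condition) |
| Section 16, end-of-trial CTP and MR | Limited: "will be done if a patient does not experience a primary endpoint before the end of trial" |
| Post study Follow-up Period | Yes (all patients) |
| Section 17 | Silent; only treatment stops being monitored |
| Section 21.2 | Does not set visits, but needs outcomes on all randomized patients |
| Schedule of Visits and Tests | Yes (no condition, plus an event visit) |

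The imaging condition is informative. If follow-up had already ended at the endpoint, there would be no need to restrict end-of-trial CTP and MR to event-free patients. It implies that patients with an endpoint still reach the end-of-trial evaluation. Most of the text favours continuation, but nothing expressly overrides the opening sentence.

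**2. How many patients are exposed if the opening sentence is applied?**

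Inputs: 50 patients per arm (Section 21.1); 30-day stroke risk of about 4% per hemisphere (Section 3); 15% ceiling on perioperative stroke or death for site selection (Section 15). Assumptions: one operated hemisphere per patient, and the same rate in both arms. The 10.1% one-year figure in Section 3 is not used, because it counts TIA, which does not trigger the endpoint.

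Expected patients per arm = 50 × rate:
- 4%: 50 × 0.04 = 2.0
- 15%: 50 × 0.15 = 7.5

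Chance of at least one such patient among 100 at 4%: 1 − 0.96^100 = 0.983.

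For the effect on a score, suppose survivors of an event worsen by d more mRS points than event-free patients. Dropping them understates the arm's mean worsening by rate × d. With d assumed to lie between 1 and 3:
- 4%: 0.04 × 1 = 0.04 to 0.04 × 3 = 0.12 points
- 15%: 0.15 × 1 = 0.15 to 0.15 × 3 = 0.45 points

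These are upper values for each rate. They treat every event patient as a survivor with no usable score, although those who die have no later score under any rule.

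**The case against.** The strongest reply is that the opening sentence is loosely worded and the rest of the protocol corrects it. The unconditional evaluations, the event visit, the post-trial follow-up of all patients and the imaging exception all assume that patients with an endpoint remain in follow-up. This stands to a large extent, and it limits the point to a contradiction. It does not remove the point: the sentence on best effort mentions neither post-event visits nor any exception to the sentence before it.

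A reader might infer more than the documents support:
- *That the later data will certainly be lost and only event-free patients compared.* No passage says so. Scores before the event and at the event visit are still collected, and Section 21.2 keeps every randomized patient.
- *That any stroke ends follow-up.* Under Section 6.1 an ischemic stroke after day 30 is not a primary endpoint. Sections 17 and 21.7 describe the endpoint differently (stroke on the surgery side; one-year stroke or death). These must be reconciled, since they change who would be stopped.
- *That a whole treatment difference in mRS would vanish.* That follows only if all event-free patients are assumed unchanged and all event patients are removed, so the assumptions force the result.
- *That the mRS form loses deaths because its last category is* "Severe disability; bedridden, incontinent and requiring constant nursing care and attention". Deaths are recorded as endpoints and serious adverse events. How death enters an mRS analysis is commonly left to the SAP, which is not at hand.

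**Conclusion.** The point holds as an internal contradiction with a real but conditional consequence. The primary time-to-first-event analysis is not affected. The secondary functional and event comparisons would have outcome-dependent missing data if sites follow the opening sentence of Section 16. Those at risk are survivors of a stroke within 30 days or of a later ipsilateral hemorrhage. Illustratively they number about 2 per arm at 4% and up to 7.5 per arm at 15%, any deaths included. The range rests on background rates quoted in the protocol for other purposes and on equal rates in the two arms. The size of any shift in mean mRS rests on an assumed worsening and is only a guide. The consequence is worth preventing because data never collected cannot be recovered in the analysis.

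**What to change.** Replace the opening sentence of Section 16 with: *All patients will be followed, with all scheduled clinical assessments and event collection, to the end of the trial whether or not a primary endpoint occurs; only the time-to-first-event clock for the primary analysis stops at the event.*

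The end-of-trial imaging condition is explicit and separate. The new sentence covers clinical assessments and event collection and leaves that condition as it is. It also fixes no number of months, so it does not prejudge the 1-year or 2-year window for TIA and contralateral infarction, which needs its own correction. The handling of death in the mRS analysis can be left to the SAP.

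The cost is one sentence. The visits are already in the schedule. A few patients, some of them disabled and harder to bring in, would have to complete visits they might otherwise miss.

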	
Disease, Type I Diabetes Mellitus, Type I Neurofibromatosis et al)
 
 
• Patient whose initial onset was marked by ischemia but subsequently suffered from intracranial hemorrhage
 
• Emergent evacuation of intracerebral hematoma damaging superficial temporal artery or cortical artery
 
• Emergent decompressive craniotomy causing automatically developed indirect revascularization
 
• Good collateral networks formed by spontaneous anastomosis between extracranial and intracranial vessels before surgery
 
• Life expectancy < 1 years
 
• Pregnancy
 
• Unstable angina or myocardial infarction with recent 6 months
 
• Blood coagulation dysfunction
 
• Allergic to iodine contrast agent
 
• Abnormal liver function (alanine transaminase (ALT) and/or aspartate aminotransferase (AST) > 3 times of normal range)
 
• Serum creatinine > 3 mg/dl
 
• Poorly controlled hypertension (systolic BP > 160 mmHg, diastolic BP > 100 mmHg)
 
• Poor glucose control (fasting blood glucose > 16.7 mmol/l)
 
• Concurrent participation in any other interventional clinical trial
 
• patients refused to participate in the study
 

Sample Size
	
Finally, 100 patients are randomized (1:1) to two groups, 50 of them will undergo direct bypass guided by multimodal neuronavigation, while others will undergo empirical direct bypass procedure.

Follow-up	The face-to-face interview will be performed by study neurologists at 7 days, at discharge, at 3 months, at 6 months and at 12 months (or by telephone) after the recruitment of patients.
------------------	--

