## **6. Study Endpoints**

### **6.1. Primary Endpoint**

All strokes & death within 30 days post-surgery and ipsilateral hemorrhage afterwards

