## 17. Management of Ischemic Events with Temporary Signs during Follow-up

If a patient in either treatment arm develops a potential clinical neurological event (TIA, ischemic stroke), an adjudication packet will be produced by the site within 72 hours. Vascular imaging including angiography will be at the discretion of study neurosurgeon. If primary endpoint occurs, MRI will be performed. Since the most effective therapy is unknown for MMD patients with frequently TIA or recently ischemic stroke, it will be not recommended for patients to receive multimodal neuronavigation bypass or empirical bypass. However, the patient's risk factors should be in target goals.

If patients in the both arms experience TIA or ischemic stroke postoperatively associated with MRI proven infarctions, continued medical therapy alone for them will be recommended by study investigators consisting of neurosurgeons. Decompressive craniectomy will be not recommended to patients without risk of cerebral hernia who have an ischemic stroke.

Additionally, if patients have reached a primary endpoint, that is, stroke in the territory of surgery side, any treatment after occurrence of stroke will be not monitored by investigators and at the discretion of treating physicians.

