## APPENDIXS

### Study Design Chart

**Study Flow Chart**

**Schedule of Visits and Tests**

	Visit 1	Visit 2	Visit 3	Visit 4	Visit 5	Visits after 1 year	Event visit
Assessments	Screening/Randomize	At discharge	At Day 90 ±7d	At Day 6 months ±14	At 1 year ± 1 month	Every 12 months ±1 month	
Informed Consent	X						
Eligibility criteria	X						
Patient Randomization	X						
Relevant medical history	X						
Demographics	X						
MRI	X						
CTP	X						
DSA before Surgery							
Vital signs	X						X
Modified Rankin Score	X	X	X	X	X	X	X
NIHSS	X	X	X	X	X		X
Modified Barthel Score	X	X	X	X	X		X
Process Core Labs	X						
MRI after surgery		X	X	X	X		
CTP after surgery		X	X	X	X		X
DSA after surgery		X	X	X			X
Compliance reminder			X	X	X	X	X
Current Medications	X	X	X	X	X	X	X
Risk factor Management	X		X	X	X	X	X
AEs, SAEs and Endpoints		X	X	X	X	X	X

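### No scheduled contact falls at postoperative day 30, where the primary endpoint changes definition, so capture between discharge and the 3-month visit rests on event reports and recall

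*Protocol*

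**What the plan says.** Section 6.1 defines the primary endpoint as "All strokes & death within 30 days post-surgery and ipsilateral hemorrhage afterwards"; the synopsis and Section 4 agree. The first secondary endpoint in Section 6.2 is "All kinds of adverse events related to surgery within 30 days". Both depend on postoperative day 30.

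Section 16 places the follow-up interviews "at discharge, at 3 months, at 6 months and at 12 months (or by telephone) after the recruitment of patients". Its visit table counts from randomization as Day 0, gives the 3-month visit as Day 83-97, and leaves the discharge date open: "Based on the number of hospitalization days". The synopsis adds one earlier contact, "at 7 days, at discharge, at 3 months, at 6 months and at 12 months (or by telephone) after the recruitment of patients", which is also counted from recruitment. The appendix schedule collects "AEs, SAEs and Endpoints" at discharge, then at Day 90 ± 7, and at an unscheduled event visit. No list has a contact at or near postoperative day 30.

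The 3-month visit looks back: "Information will be collected on medications, risk factors, and events of interest since the last visit". For a potential neurological event, with TIA and ischemic stroke as the only examples named, Section 17 says that "an adjudication packet will be produced by the site within 72 hours". Section 20 adds that source documents are copied when a patient with an event is treated outside the study sites.

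**The concern.** Under Section 6.1, the date of an event can decide whether it counts at all. An ischemic stroke on postoperative day 29 is a primary event; the same stroke on day 31 is not. If it is ipsilateral, it is not a listed secondary event either, because Section 6.2 names only contralateral infarctions and ipsilateral TIA. A contralateral infarction would move from the primary to a secondary endpoint. A symptomatic ipsilateral hemorrhage counts on either side of the cut, so for that event the date affects only the event time in the Cox model.

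The visit clock starts at randomization and the 30-day clock at surgery, so the schedule never marks the boundary. Nobody is due to ask the patient anything when the 30-day window closes. A mild or brief deficit that was not reported when it occurred is first asked about at 3 months, and its onset date then rests on memory. The same applies to surgical adverse events after discharge that were not neurological or were managed elsewhere.

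Loss to follow-up adds to this. Section 21.8 censors a lost patient at the last contact at which freedom from the primary endpoint was known. A patient lost after an uneventful discharge is therefore censored at discharge, and the rest of the 30 days, which Section 3 calls the period of highest stroke risk, is not observed.

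**Working it through.** **Inputs.** One month = 30 days, with windows of ±7, ±14 and ±30 days (Section 16). 30-day stroke risk of about 4% per hemisphere (Section 3). Ceiling of 15% perioperative stroke or death for site selection (Section 15). 100 patients (Section 21.1). Not stated, so assumed over a range: S, days from randomization to surgery; D, postoperative day of discharge.

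**Reproducing the plan's visit windows.** 3 × 30 ± 7 = Day 83-97; 6 × 30 ± 14 = Day 166-194; 12 × 30 ± 30 = Day 330-390. All agree with Section 16.

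**Delay from postoperative day 30 to the next scheduled contact.** Postoperative day 30 is study day S + 30, so the delay is (83 to 97) − (S + 30).

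| S (assumed) | Postoperative day 30 falls on | Delay to 3-month visit |
|---|---|---|
| 0 | Day 30 | 53-67 days |
| 7 | Day 37 | 46-60 days |
| 14 | Day 44 | 39-53 days |
| 30 | Day 60 | 23-37 days |

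**Part of the 30 days after discharge with no scheduled contact.** This is 30 − D: 23 days for D = 7, 20 for D = 10, 16 for D = 14, 9 for D = 21, and none for a patient still in hospital on day 30. The synopsis's 7-day contact does not close the gap. Even if it were counted from surgery, 30 − 7 = 23 days would remain for a patient discharged by then.

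**Weight of one misplaced event.** With one operated hemisphere per patient (assumption), 0.04 × 100 = 4 expected strokes within 30 days, and one is 1/4 = 25% of them. At the ceiling, 0.15 × 100 = 15 strokes or deaths, and one is 1/15, about 7%. These figures show how much one error weighs. They do not estimate how many errors will occur, and the protocol gives nothing from which to estimate that.

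**The case against.** The strongest reply is that the protocol does not leave this interval empty. It has the 72-hour adjudication packet and MRI when a primary endpoint occurs (Section 17), an event visit marked for adverse events and endpoints (schedule), copied outside records (Section 20) and committee adjudication (Section 21.3). This largely stands. A reader might infer that 30-day events can only be reconstructed weeks later and cannot be dated. The documents do not support that for deaths or for strokes that bring a patient to hospital. What remains is that every one of these routes starts with a report, and that hemorrhage and non-neurological adverse events are not named in the 72-hour rule.

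Three other stronger readings also fail.

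- An infarct first seen on the 3-month MRI might look like an undatable primary event. Without symptoms it meets none of the appendix stroke definitions, which require a new or worsening deficit, or a hemorrhage with neurological symptoms.
- Ascertainment might be thought to differ by arm through different discharge times. Nothing in the protocol says so: both arms have direct bypass by the same surgeon (Sections 5 and 21.4) and share one follow-up schedule.
- The delay of 53-67 days might be taken as fixed. It holds only for surgery on Day 0, which looks unlikely for patients on aspirin, because Section 12 has both arms suspend it 7 days before the procedure.

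Finally, Section 21.7 describes the primary endpoint as stroke or death over one year, and Section 17 as stroke on the operated side. Under Section 21.7 the day-30 cut would disappear from the primary endpoint. That conflict has to be settled, but the synopsis, Section 4 and Section 6.1 all use the day-30 rule, and the adverse-event endpoint closes at 30 days in any case.

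**Conclusion.** The gap is real and follows from the protocol alone: a date-dependent primary endpoint and a 30-day secondary endpoint, with no scheduled contact from discharge (or the synopsis's day 7) until Day 83-97. The exposure is limited to symptomatic strokes that are mild, transient or unreported, and to non-neurological surgical adverse events. The delay after postoperative day 30 is 23-67 days for surgery between day 30 and Day 0, and there is no gap for a patient still in hospital on day 30. One misplaced event is about 7% to 25% of the expected 30-day events, given the protocol's own rates and one operated hemisphere per patient. How often this would happen cannot be derived. This should be changed because the remedy is cheap and the primary endpoint has few events; it is not evidence that the result would be biased toward either arm.

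**What to change.** Add to Section 16 and to the appendix schedule a scripted telephone call counted from the date of surgery, at postoperative day 30 to 37 and not before day 30. Existing follow-up staff would make it. The script asks about death, new neurological symptoms with onset date, readmission and surgical adverse events. Any positive answer triggers the existing event visit.

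Keep the 30-day endpoint and adverse-event forms open to in-window events learned of later, and to patients not reached at the call. Closing them at the call would conflict with the best-effort collection of endpoint information that Section 16 promises.

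Reconcile the descriptions of the primary endpoint in Sections 17 and 21.7 with Section 6.1, so that it is settled whether day 30 is the cut.

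The cost is about 100 short calls and one CRF page, a small addition to site workload.

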## 11. Image Data Evaluation

Considering the quality of the angiographic images in the trial, we will select participating sites which are available to have access to state-of-the-art cerebral angiography facilities. The investigators in each site will be trained and certificated for image acquisition and measurement before the startup phase of the trial.

The angiographic imaging showed internal carotid artery stenosis/occlusion site, moyamoya vessels and vascular compensatory level. MRI should contain structure sequence and ASL sequence.

When a patient is enrolled in the trial, core lab will obtain CD copies of angiographic images, CT perfusion and MRI for central review. Images of the cerebral artery, CT perfusion and MRI post revascularization surgery also must be sent to core lab for central review.

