### **21.2. Description of analysis sets**

All patients who have been randomized to study treatment will be included irrespective of their protocol adherence and continued participation in the study. Patients will be analyzed based on the initial treatment assignment irrespective of whether the event occurred before or following discontinuation of study medication. Patients who withdraw consent to participate in the study will be included up to the date of their study termination except for vital status known through public records (for use in the analysis of all cause death). All efficacy variables will be analyzed using the full analysis set (FAS).

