## 21.7. Interim analyses

One interim analysis will be planned and conducted by the Data Monitoring Committee following the accrual and confirmation by adjudication of 50% of planned primary events. The stopping rule of Lan-DeMets approach to O'Brien-Fleming will be adopted for stopping for efficacy or futility. The efficacy stopping boundary at the interim analysis is a 2-sided p-value <0.0015 for the primary endpoint (one-year stroke or death). The final last level of significance with one interim analysis will therefore be 0.0489, with the family wise error rate controlled at 5.00%. The trial would be halted due to futility if nominal critical point (Standardized Z scale) for the primary endpoint crosses the internal boundary for futility ( $\pm 0.595$ ). It will be determined by the executive committee that the trial will be continued or stopped due to the overwhelming efficacy or futility after recommendation of Data Safety Monitoring Board.

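### Section 16 withholds the end-of-trial MR, and with it the final ASL-CBF value, from patients who have had a primary event, while the visit schedule marks the 1-year MRI for everyone

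*Protocol*

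**What the plan says.** - **Protocol Section 16 (end-of-trial evaluations):** CTP and MR "will be done if a patient does not experience a primary endpoint before the end of trial". The same list asks for mRS, NIHSS, Barthel and MoCA at the end of trial with no such condition. The MR at 3 and 6 months also carries no condition.
- **Appendix, Schedule of Visits and Tests:** the row "MRI after surgery" is marked at discharge, day 90, 6 months and 1 year, and the postoperative CTP row is also marked at 1 year. No event-free condition is attached to either.
- **Section 11:** "MRI should contain structure sequence and ASL sequence".
- **Section 6.2:** a secondary endpoint is "The changes from baseline in CBF measured by ASL at 7 days, 3 months, 6 months, 12 months or end of trial", with no restriction to event-free patients.
- **Section 21.2:** every efficacy variable is assigned to the full analysis set, which keeps all randomized patients under their assigned arm.
- **Section 17:** "If primary endpoint occurs, MRI will be performed".

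**The concern.** Two parts of the protocol give a site different instructions for the same scan. A patient who has survived a primary event is due an MRI at 1 year under the schedule, but Section 16 gives no basis for doing one.

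This matters because the ASL sequence sits inside the MRI: without the MR there is no final CBF value. Under Section 16, whether that value exists depends on a post-randomization outcome, and Section 4 expects that outcome to be less frequent in the navigation arm. The observed final CBF values would then come from two groups that are no longer the randomized ones.

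How to handle a missing value can be left to the statistical analysis plan. Whether the scan is acquired is settled in the protocol, and an untaken scan cannot be recovered at analysis.

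**Working it through.** **Step 1. Are the two instructions about the same visit?** The protocol does not say outright that end of trial is the 12-month visit, so this is an inference. Twelve months is the last visit in the Section 16 table. Yearly contact then starts after the end of trial in the post-study paragraph of Section 16, and after 1 year in the schedule. The two texts line up only if end of trial is the 12-month visit.

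**Step 2. Does another source supply the final CBF value?** The MRI ordered in Section 17 is taken when the event occurs. The 3- and 6-month scans are earlier time points. None of them is an observed 12-month value.

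**Step 3. How many patients?** The protocol states no rate for its primary endpoint, so there is no figure to reproduce. The nearest is in Section 3 (surgical treatment): a 30-day stroke risk of about 4% per hemisphere. It is only a proxy, as it leaves out non-stroke deaths and later ipsilateral hemorrhage. Section 21.1 gives 50 patients per arm. Let p_emp and p_nav be the event rates in the empirical and navigation arms.

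Patients without a final scan = 50 × p_emp + 50 × p_nav

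- 4% vs 4%: 2 + 2 = 4
- 4% vs 2%: 2 + 1 = 3
- 4% vs 0%: 2 + 0 = 2

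Fatal events are counted here, although those patients cannot be scanned under any rule. The 2% and 0% rates are assumptions.

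**Step 4. How much bias if only observed final values are compared?** Let d be the mean CBF change in event patients minus that in event-free patients, in SD units and equal in both arms. The documents give no value, so 0.5 to 1 SD in either direction is assumed.

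Arm mean over all patients = event-free mean + p × d

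Bias of the event-free comparison (navigation minus empirical) = (p_emp − p_nav) × d

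| Rates (emp vs nav) | Size of d = 0.5 | Size of d = 1 |
|---|---|---|
| 4% vs 4% | 0 | 0 |
| 4% vs 2% | 0.02 × 0.5 = 0.010 | 0.02 × 1 = 0.020 |
| 4% vs 0% | 0.04 × 0.5 = 0.020 | 0.04 × 1 = 0.040 |

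The sign follows d.

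**Step 5. Compared with sampling error.** Standard error with 50 per arm = √(1/50 + 1/50) = 0.200 SD. With the event patients removed it is √(1/48 + 1/49) = 0.203 for 4% vs 2%, and √(1/48 + 1/50) = 0.202 for 4% vs 0%. Where the rates differ, bias divided by 0.200 runs from 0.010/0.200 = 5% to 0.040/0.200 = 20% of one standard error.

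**The case against.** **The conflict is soft.** A visit grid is a summary, and conditions often stand in the body text. Section 16 also does not forbid MR after an event. Both points are fair. But nothing in the grid refers to a condition, and the unconditional clinical scales in the same Section 16 list show that event patients are still expected to be assessed at that visit. Leaving out imaging after an event could be deliberate, but the protocol gives no reason for it.

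**Event patients need not drop out of the analysis.** This stands in part. Section 3 puts the highest stroke risk in the first 30 days, so many surviving event patients would have 3- and 6-month ASL values taken after the event. A repeated-measures model could keep them in the full analysis set. A reader might infer that the final comparison must cover only event-free patients and cannot be a full-analysis-set comparison. The protocol does not support that: it fixes no complete-case analysis for CBF, and Section 21.2 defines who is analyzed, not that every measurement exists. What remains is that the model would rest on a missing-data assumption that the scheduled scan would largely remove.

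**A larger bias could be claimed.** A reader might take the 10.1% in Section 3 or the 15% in Section 15 as event rates. The first counts TIA, which is not in the primary endpoint. The second is a ceiling for site selection, not an expected rate. Neither matches Section 6.1, so no bias figure is based on them.

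**The trigger is also unclear.** Section 17 describes the primary endpoint as "if patients have reached a primary endpoint, that is, stroke in the territory of surgery side", and this differs from Section 6.1 for strokes after day 30. That inconsistency is a matter of its own and adds no weight here.

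**Some scans will be lost anyway.** The 12-month contact may be by telephone, and severely affected patients may not tolerate a scan. This is true, but it does not justify withholding the scan by rule.

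**Conclusion.** The contradiction between Section 16 and the schedule is real and should be resolved, but its effect is minor. It concerns the last time point of one secondary endpoint, in a trial that Section 21.1 calls exploratory, and it leaves the time-to-first-event primary analysis untouched.

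The size rests on three assumptions: that the 4% proxy resembles the primary event rate, that CBF change differs by 0.5 to 1 SD between event and event-free patients, and that only observed final values are compared. The bias vanishes if the arms have equal event rates and equal d.

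A reader might infer that the restriction hides a benefit of navigation, since event patients could be expected to have poorer flow. That needs both fewer events in the navigation arm and a negative d. The first is the trial's hypothesis and the second is not documented, so the direction is not established.

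**What to change.** Reconcile Section 16 with the Schedule of Visits and Tests by removing the event-free condition on MR. Section 16 could state that MR including ASL is obtained at 12 months/end of trial in all surviving, consenting patients where feasible, whether or not a primary endpoint event has occurred. The CTP condition in the same sentence must also be reconciled with the schedule. It would help to say explicitly that end of trial is the 12-month visit, if that is what is meant.

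The cost is a change of wording and, on the 4% proxy, about 2 to 4 MR sessions (fewer once deaths are taken out), of a type the schedule already lists at 1 year. The remaining downside is that some severely affected patients will still have no scan, so the statistical analysis plan will still need a rule for missing CBF values.
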